2.4.3 Primary analysis

Non-inferiority testing of Restylane Defyne relative to Restylane will be assessed on the 95% confidence interval approach with a non-inferiority margin of 15%. The confidence interval will be constructed for the difference (Restylane minus Restylane Defyne) in response rates at the 6 months follow-up visit (Table 8-1 and Table 8-2). Non-inferiority will be declared if the two-sided 95% interval is fully below 15%, i.e., the upper bound of the interval is less than 15% in both the FAS and PP populations.

To assess the robustness of the results using the MI method, LOCF will be used as an alternative imputation method. The same summary of primary analysis results will also be presented for observed cases (OC), (Table 8-1).

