4.4 Randomization and blinding

4.4.1 Randomization

Each subject will be randomized to one of two treatment sequences; either Restylane Defyne in the subject's right NLF followed by Restylane in the subject's left NLF, or Restylane in the subject's right NLF followed by Restylane Defyne in the subject's left NLF. Treatment will always start in the subject's right NLF. The randomization will be stratified by site and the randomization list will be computer generated under the supervision of a designated statistician.

Each subject will be assigned a subject number as they arrive for the treatment visit. Randomization will be assigned via the electronic case report form (eCRF) system when all inclusion criteria and exclusion criteria have been verified. At the time of randomization, the subject's initials, date, subject number, treatment sequence, and the signature of the Investigator must be documented in a randomization log. All treatment information will be kept by the treating Investigator during the study not to be disclosed to the blinded evaluator.

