1.1.1 Study design

This is a randomized, evaluator-blinded study to evaluate the efficacy and safety of Restylane Defyne (with lidocaine) compared to Restylane (without lidocaine) for correction of moderate to severe nasolabial folds (NLFs) in subjects of Chinese origin, men or women aged 18 years or older.

The study will be conducted at 4 sites located in China, and subjects with a Wrinkle Severity Rating Scale (WSRS) score of either 3 or 4 on both sides, as assessed by the Blinded Evaluator, will be enrolled. The subjects will be followed for up to 14.5 months.

Blinding will be accomplished by a Blinded Evaluator, to whom randomization and treatment are concealed, to evaluate the WSRS score. The treating Investigator will not be blinded. To minimize inter-observer variability, a subject should preferably be assessed by the same individual at the initial Baseline determinations and all follow-up evaluations.

For more details regarding the study, and references, please see the Clinical Study Protocol (CSP), MA-29708.

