1.1.2 Number of subjects and randomization

Approximately 175 subjects will be enrolled and treated with Restylane Defyne in one NLF and Restylane in the opposite NLF, as randomly assigned to one of the two possible treatment sequences:

[figure not shown]
- Restylane Defyne in the subject's right NLF followed by Restylane in the subject's left NLF, or
- Restylane in the subject's right NLF followed by Restylane Defyne in the subject's left NLF.

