2.4 Efficacy Analysis

2.4.1 *Data sets analyzed*

All efficacy variables will be analyzed using the FAS population. The primary analysis will be repeated using the PP population. If it is deemed necessary, other analyses will be repeated using the PP population.

2.4.2 *Handling of missing data*

As the study design is intra-individual, in which the outcome of both treatments to be compared is available on each subject, it is expected that when a data is missing, it will be missing for both NLFs in most of the cases. A majority of the deviations from the protocol can be expected to affect both NLFs and evaluations of the same subject the same way.

 GALDERMA	Title SAP, 43CH1508, Restylane Defyne NLF	Doc id MA-31549
--	--	----------------------------------

Effective date: 2017-02-13 08:27

Effective

Version: 1.0

FAS analyses of WSRS scores in the primary analysis will use multiple imputation method (MI) as the primary method for imputing missing values. Rather than imputing each missing observation by a single value, this approach represents a random sample of the missing values, and therefore accounts for the prediction uncertainty of the unknown missing values. Last observation carried forward (LOCF) will be used as an alternative imputation method.

Safety and PP analyses will be presented based on observed cases, i.e., no imputation of missing values will be performed.

(i) Use of MI

The imputation using MI will assume a Missing Completely at Random (MAR) mechanism. The MI procedure of the SAS® system will be used to generate five sets of data with missing values imputed from observed data. It is expected that the pattern of missing data will be monotonic, with slight deviations being corrected by the Markov Chain Monte Carlo (MCMC) method of the MI procedure. Linear regression will be employed to model the missing WSRS score, with the following covariates included in the imputation model: treatment and non-missing data from earlier time points (Baseline, Week 2, and Month 3). The imputed datasets will be analyzed using the methodology described for the primary analysis of response rates at Month 6. The results from the analysis of the multiple imputed datasets will be presented as appropriate. The seed number to be used will be 431508.

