2.4.4 Subgroup analysis of primary endpoint

Graphical presentation, such as blobbogram, will be used to explore the differences in WSRS response rates between treatments by site, with corresponding 95% confidence intervals (Graph 8-1 and Graph 8-2).

[figure not shown]
 GALDERMA	Title SAP, 43CH1508, Restylane Defyne NLF	Doc id MA-31549
--	--	----------------------------------

Effective date: 2017-02-13 08:27

Effective

Version: 1.0

CCI

[figure not shown]

 GALDERMA	Title SAP, 43CH1508, Restylane Defyne NLF	Doc id MA-31549
--	---	---------------------------

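### The primary difference pools both side sequences although sequence is what is randomized; using sequence would tighten the interval slightly and is a refinement, not a validity repair

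*SAP*

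**What the plan says.** Protocol 4.4.1 sets up the allocation, here cut short: "Each subject will be randomized to one of two treatment sequences; either Restylane Defyne in the subject's right NLF followed by Restylane in the subject's". The sentence ends with the opposite fold and then gives the mirror-image sequence. The section adds: "Treatment will always start in the subject's right NLF". Side and injection order therefore coincide, and the random element is which product falls on the right, first-injected side. The list is stratified by site ("The randomization will be stratified by site and the randomization list will be computer generated under the supervision of a designated statistician"). No block size and no allocation ratio between the two sequences is given. SAP 1.1.2 gives the size: "Approximately 175 subjects will be enrolled and treated with Restylane Defyne in one NLF and Restylane in the opposite NLF".

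For the primary analysis, SAP 2.4.3 says: "The confidence interval will be constructed for the difference (Restylane minus Restylane Defyne) in response rates at the 6 months follow-up visit". Non-inferiority requires the upper 95% limit to lie below 15% in both FAS and PP. The visible text has no term for sequence or side. It also names no interval method and does not say that the interval is paired.

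The imputation model in SAP 2.4.2(i) uses "treatment and non-missing data from earlier time points". Site enters the visible efficacy analysis through a graph that "will be used to explore the differences in WSRS response rates between treatments by site" (SAP 2.4.4). None of the visible table shells in SAP Appendix E reports response by side or sequence.

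**The concern.** An analysis normally reflects the way subjects were randomized. Suppose the right or first-injected fold does better or worse than the left, through injector handedness, facial asymmetry or order. That effect enters the within-subject difference with opposite signs in the two sequences. Pooling the sequences leaves it in the spread of the differences. If the sequences are unequal in number, a part of it also stays in the estimate.

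Equal numbers are not assured in the sets that decide the trial. No block size is stated, withdrawn subjects are not replaced (Protocol 5.5), and PP drops subjects for the deviations in SAP Table 2-1. At stake is a little precision, and a prespecified answer to a question that would be awkward to settle after the fact if the upper limit fell close to 15%.

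**Working it through.** **Inputs.** From the documents: n = 175 (SAP 1.1.2), two sequences with the right fold first (Protocol 4.4.1), a two-sided 95% interval and a 15-point margin (SAP 2.4.3). Assumed: the proportion of discordant pairs ψ, the side effect s, and a paired Wald-type interval. The assumptions behind 175 are blacked out in Protocol 10.10 and SAP 2.7, so that figure cannot be reproduced. This is not a fault of the plan.

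**Model.** Let d be a subject's Restylane response minus Restylane Defyne response (−1, 0 or 1), τ the true product difference and s the right-minus-left effect. The mean of d is τ − s with Defyne on the right (n₁ subjects) and τ + s with Defyne on the left (n₂ subjects). Hence:

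- Expected pooled mean = τ − s(n₁ − n₂)/n. This equals τ when n₁ = n₂, and also on average over the randomization.
- At τ = 0 with balanced sequences, the pooled variance of d is ψ and the within-sequence variance is ψ − s².

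**Width.** Unadjusted half-width = 1.96 × √(ψ/175). Adjusted half-width = 1.96 × √((ψ − s²)/175). For example, with ψ = 0.30 and s = 0.10, 1.96 × √(0.30/175) = 8.12 points and 1.96 × √(0.29/175) = 7.98 points.

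| ψ | Unadjusted | Adjusted, s = 5 points | Adjusted, s = 10 points | Gain |
|---|---|---|---|---|
| 0.15 | 5.74 | 5.69 | 5.54 | 0.05; 0.19 |
| 0.20 | 6.63 | 6.58 | 6.46 | 0.04; 0.17 |
| 0.30 | 8.12 | 8.08 | 7.98 | 0.03; 0.14 |

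A side effect of 15 points would give gains of 0.31 to 0.45 points over the same range of ψ.

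**Chance shift.** Under simple randomization n₁ − n₂ has SD √175, about 13. The shift then has SD s/√175, which is 0.38 points for s = 5 and 0.76 points for s = 10. For one realized list:

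| Imbalance n₁ − n₂ | s = 5 points | s = 10 points |
|---|---|---|
| 1 | 0.03 | 0.06 |
| 13 (1 SD) | 0.37 | 0.74 |
| 26 (2 SD) | 0.74 | 1.49 |

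**These are one term.** The extra variance in the unadjusted interval is ψ/175 − (ψ − s²)/175 = s²/175. The variance of the chance shift is (s/√175)² = s²/175. Under simple randomization the wider interval is what pays for the shift. Under balance the width remains and there is almost no shift to pay for.

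**Simulation.** 175 subjects, 4 sites, correlated pairs, a paired Wald interval, simple randomization or blocks of four within site, and side effects of 0, 5 and 10 points (8,000 runs for type I error, 4,000 for power):

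- Average bias of the unadjusted difference: at most 0.07 points, which is Monte Carlo noise.
- Type I error at a true 15-point inferiority (75% v 60%): 2.2% to 2.6% unadjusted, 2.4% to 2.7% adjusted.
- Power with no true difference (70% each): 96.8% to 97.5% unadjusted, 97.2% to 97.6% adjusted.
- With no side effect and simple randomization, the adjusted full width at a true 15-point inferiority was 15.30 points against 15.25. The adjustment is therefore nearly, but not exactly, free.

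**The case against.** The strongest reply is that nothing is broken. Each subject receives both products and side is randomized, so a side effect is balanced between products by design. Ignoring it can only make non-inferiority slightly harder to declare on average. The side effects used above are assumptions with no support in the documents, and the design works towards symmetry: inclusion criterion 4 requires the same WSRS grade on both sides, and Protocol 6.6.1 standardizes volume, time, depth and technique across the folds. A list stratified by site is probably blocked, which would keep the imbalance small. An equal-weight estimate also departs from the raw rate difference in SAP Tables 8-1 and 8-2 when the sequences are unequal. All of this stands, and it is why the point is minor. Equal entry grades do not, however, rule out an order effect, and blocking does not protect PP after exclusions.

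A reader might infer more than the documents support:

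- **That site adjustment would also remove noise.** A site main effect cancels in a within-subject difference. Only a product-by-site interaction could matter, and SAP 2.4.4 already displays it.
- **That the imputation model is deficient for lacking side.** Product and earlier scores are in it, and SAP 2.4.2 expects missing data to affect both folds in most cases. No material effect has been shown.
- **That no side analysis exists anywhere.** Text is blacked out after Protocol 10.4.1 and SAP 2.4.4, so this can be said only of the visible text.

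**Conclusion.** The visible primary analysis does not use the sequence that Protocol 4.4.1 randomizes, and using it would be a small improvement. For side effects of 5 to 10 points and 15% to 30% discordant pairs, the gain is about 0.03 to 0.2 points of half-width against a 15-point margin. With no side effect there is essentially nothing to gain.

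It is tempting to conclude that an ignored side or order effect distorts the non-inferiority decision, or that the wider interval and the chance shift are two separate harms. Neither follows. There is no average bias and no inflation of type I error, and the width and the shift are the same s²/175 term. What remains is a matter of efficiency and of matching the analysis to the design. The sizes rest on the assumed s and ψ, on n = 175 and on a paired interval. In a smaller PP set, n changes accordingly.

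**What to change.** In SAP 2.4.3, define d for each subject as Restylane minus Restylane Defyne response. Take its mean and variance in each randomized sequence (d̄₁, v₁, n₁ and d̄₂, v₂, n₂). Estimate the difference as (d̄₁ + d̄₂)/2, with variance (v₁/n₁ + v₂/n₂)/4 and limits at ±1.96 standard errors. Apply this to FAS (in each imputed dataset, then combined) and to PP. It also puts the pairing of the two folds in writing.

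Keep the unadjusted paired difference as a sensitivity analysis, and add a table of response rates by side. Footnote Tables 8-1 and 8-2 to say that, with unequal sequences, the estimate can differ slightly from the raw difference in rates. Adding side to the imputation model is optional, and no site term is needed for this purpose.

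The cost is a short SAP paragraph, a few lines of code, one extra table and the footnote. Data collection does not change.

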7.2 Wrinkle severity rating scale

The WSRS is a validated photograph-based outcome instrument that is designed specifically for quantifying facial folds (Table 2). Scoring of fold severity is based on visual assessment of the length and apparent depth of the NLF at a certain time-point and the result is not based on a comparison to the baseline or pre-treatment appearance. Each score in the WSRS is exemplified by a photograph of NLFs²² (Appendix 4).

Live assessments will be performed through-out the study.

Table 2. Wrinkle severity rating scale

Grade	Description
1	Absent: No visible fold; continuous skin line.
2	Mild: Shallow but visible fold with a slight indentation; minor facial feature. Implant is expected to produce a slight improvement in appearance.
3	Moderate: Moderately deep folds; clear facial feature visible at normal appearance but not when stretched. Excellent correction is expected from injectable implant.
4	Severe: Very long and deep folds; prominent facial feature; less than 2-mm visible fold when stretched. Significant improvement is expected from injectable implant.
5	Extreme: Extremely deep and long folds; detrimental to facial appearance; 2- to 4-mm visible V-shaped fold when stretched. Unlikely to have satisfactory correction with injectable implant alone.

The blinded evaluator will evaluate WSRS at the screening and baseline visits to verify inclusion criteria 4 and further evaluate the WSRS before the initial treatment. The WSRS will also be assessed by the blinded evaluator at each follow-up visit (4 weeks after initial treatment and touch-up, if applicable, as well as 3, 6, 9, and 12 month after the last treatment) for efficacy assessment. At the Week 4 follow-up visit after the initial treatment, the WSRS assessment will be used for treatment guidance, e.g., to decide if touch-up treatment should be performed. A clinically significant improvement is defined as ≥ 1 grade improvement in the WSRS.

Each NLF (right/left) will be evaluated separately, thus generating two wrinkle severity score results per subject. A subject should preferably be assessed by the same blinded evaluator throughout the entire study.

When treatment is administered at the same visit as the WSRS assessment, it is important to assess wrinkle severity prior to injection.

[figure not shown]

Effective

Version: 5.0

Effective date: 2017-07-05 06:37

CCI

Effective date: 2017-07-05 06:37

Effective

Version: 5.0

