2.2 Analysis Populations

The following populations will be defined:

- Full Analysis Set (FAS) Includes all subjects who were injected in both NLFs. Subjects are analyzed according to the randomization assignment.
- Per protocol (PP) Includes all FAS subjects who completed the Month 6 follow-up visit without any major deviations.
- Safety Includes all subjects who were injected in at least one NLF, based on the as treated principle.

The FAS population is the primary population for all efficacy analyses. If there are any CSP deviations considered to have substantial impact on the efficacy outcome at the Month 6 follow-up visit, a PP population excluding those subjects will be defined. As this is a non-inferiority trial, non-inferiority will need to be shown in both FAS and PP analyses. Safety analysis will be performed based on the Safety population set.

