2.3 Study Subjects

2.3.1 Subject disposition

The number and percentage of subjects in each study population (FAS, PP, and Safety) will be summarized by site (including subject number) and in total (Table 4-1). Study population variables will also be presented in a data listing.

The disposition of subjects (Table 4-4) will be presented by site, and in total, including number and percentage of subjects that were

- screened
- treated,
- completed,
- withdrawn.

The number of completed and withdrawn subjects will also be accounted for by visit, along with number of expected subjects, number of screening failures, number of treated subjects, and subjects with performed WSRS assessment (Table 4-5).

Reasons for screening failures and withdrawals, if applicable, will be summarized. All withdrawn subjects will be listed individually, including site and subject number, date of treatment, last visit performed, date and reason for withdrawal (Table 4-7). Screening failures

 GALDERMA	Title SAP, 43CH1508, Restylane Defyne NLF	Doc id MA-31549
--	--	----------------------------------

will be listed by site number, subject screening number, date of screening, and reason for screening failure (Table 4-6).

2.3.2 *Protocol deviations*

Subjects with CSP deviations will be listed individually, including subject number and observed deviation, and visit number if applicable (Table 4-3). Depending on the seriousness of the deviation, the subject might be excluded from the PP population (Table 4-2), which shall be documented prior to database lock (DBL).

Definition of protocol deviations that will exclude subjects from the PP are defined (but not limited to) in Table 2-1 below.

Table 2-1: Protocol deviations

Deviation	
GENERAL	
	Visit out-of-window
*	Follow-up at 6 months after last treatment performed earlier than 1 week before the scheduled visit or later than 2 weeks after the scheduled visit.
	Visit not done
*	Follow-up at 6 months not done.
EFFICACY	
	WSRS assessed by Blinded Evaluator
*	Not done for both NLFs at 6 months after last treatment.
*	Pre-treatment WSRS not available for both NLFs.
OTHER	
	Inclusion/exclusion criteria
*	Any inclusion criteria affecting primary efficacy evaluation not met.
*	Any exclusion criteria affecting primary efficacy evaluation met.
	Treatment
*	Same product administered in both NLFs at initial treatment or touch-up.
*	Products administered in the wrong sides at initial treatment or touch-up.

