8.1 Primary analysis

8.1.1 WSRS response rate at 6 months

Table 8-1: Difference in WSRS response rates (Restylane – Restylane Defyne) at 6 months after last treatment, FAS

Analysis	Method	Treatment	N	Improved subjects		RR	RR _{Restylane} – RR _{Restylane Defyne}			
				n	%		Δ	95% LCL	95% UCL	
Primary	MI ¹⁾	Restylane Defyne								
		Restylane								
Sensitivity	LOCF	Restylane Defyne								
		Restylane								
Sensitivity	OC	Restylane Defyne								
		Restylane								

% = n/N*100

RR = response rate

Δ = difference

LCL = lower confidence level

UCL = upper confidence level

1) See the 95% confidence interval for respective treatment response rate in Table 8-3.

Table 8-2: Difference in WSRS response rate (Restylane – Restylane Defyne) at 6 months after last treatment, PP

Analysis	Method	Treatment	N	Improved subjects		RR	RR _{Restylane} – RR _{Restylane Defyne}			
				n	%		Δ	95% LCL	95% UCL	
Sensitivity	OC ¹⁾	Restylane Defyne								
		Restylane								

% = n/N*100

RR = response rate

Δ = difference

LCL = lower confidence level

UCL = upper confidence level

1) See the 95% confidence interval for respective treatment response rate in Table 8-4.

 GALDERMA	Title SAP, 43CH1508, Restylane Defyne NLF	Doc id MA-31549
---	--	--------------------

Table 8-3: WSRS response rate at 6 months after last treatment, Blinded Evaluator's assessment, FAS

Treatment	N	Improved subjects	Response rate		
		n	%	95% LCL	95% UCL
Resylane Defyne					
Restylane					

% = $n/N * 100$

LCL = lower confidence level

UCL = upper confidence level

Table 8-4: WSRS response rate at 6 months after last treatment, Blinded Evaluator's assessment, PP

Treatment	N	Improved subjects	Response rate		
		n	%	95% LCL	95% UCL
Resylane Defyne					
Restylane					

% = $n/N * 100$

[figure not shown]
LCL = lower confidence level

UCL = upper confidence level

 GALDERMA	Title SAP, 43CH1508, Restylane Defyne NLF	Doc id MA-31549
---	--	--------------------

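### The interval that decides non-inferiority has no named method, and the imputation model, result tables and per-protocol rules around it do not carry the split-face pairing

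*SAP*

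**What the plan says.** The design is paired, and the plan says so. Protocol 7.2: "Each NLF (right/left) will be evaluated separately, thus generating two wrinkle severity score results per subject". The full analysis set (FAS) in SAP 2.2 "Includes all subjects who were injected in both NLFs". SAP 2.4.2 opens: "As the study design is intra-individual, in which the outcome of both treatments to be compared is available on each subject".

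For the primary endpoint, SAP 2.4.3 states: "The confidence interval will be constructed for the difference (Restylane minus Restylane Defyne) in response rates at the 6 months follow-up visit". It fixes the 95% level, the 15% margin and the rule that the upper bound must fall below the margin in both FAS and per protocol (PP). It does not say how the interval is calculated. The text of protocol 10.4.1 is equally silent.

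Around that sentence:
- The imputation model in SAP 2.4.2 has as covariates "treatment and non-missing data from earlier time points". The imputed data are then to be analysed by the primary-analysis method, which is the one left unnamed.
- Table 8-1, "Difference in WSRS response rates (Restylane – Restylane Defyne) at 6 months after last treatment, FAS", has N, number improved and rate per product, plus the difference and its limits. Table 8-2 has the same layout for PP.
- SAP Table 2-1 removes a subject from PP if the Month 6 WSRS is "Not done for both NLFs at 6 months after last treatment". A parallel item covers the pre-treatment score.

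**The concern.** With two correlated outcomes per subject, the variance of the difference in response rates depends on how many subjects respond on one side only. An interval that ignores this treats the trial as two independent groups of 175 and discards the precision that the split-face design was chosen to provide. Non-inferiority rests on one upper bound, so the choice of method can decide a pass or a fail.

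The visible surroundings do not settle the choice. Treatment as an imputation covariate implies one record per fold, because it would be constant with one row per subject. The opposite fold's scores are then not used to predict a missing score, and the imputed pairs are less alike than real ones. The result tables lack the counts needed to rebuild a paired interval. Read literally, the PP items remove a subject only when both folds are missing, so a subject with one assessed fold, and no pair, stays in. A within-subject contrast is spelled out for injection volume and injection time (SAP 2.3.5) but not for the primary endpoint.

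**Working it through.** **Inputs.** From the documents: about 175 subjects, margin 15 points, two-sided 95% interval. Assumed, because the documents give no Month 6 rate, correlation or missing-data rate: response 75% (range 60% to 90%), within-subject correlation of response r from 0 to 0.7, and 10% missing.

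**The plan's own figure.** The inputs behind 175 are redacted, so it cannot be reproduced, and it does not reveal the method. Unpaired, 75% response, 90% power: 2 × 0.75 × 0.25 × (1.960 + 1.282)² / 0.15² gives 176. Paired, 40% discordant, 80% power: 0.40 × (1.960 + 0.842)² / 0.15² gives 140, or 175 after 20% dropout. Both are compatible.

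**Width with equal rates p.** Unpaired SE = √[2p(1−p)/N]. Paired SE = √{[b + c − (b−c)²]/N}, where b and c are the two discordant proportions. With equal rates, b + c = 2p(1−p)(1−r), so the ratio of widths is 1/√(1−r). At p = 0.75 and N = 175 the unpaired half-width is 1.96 × √(0.375/175) = 9.1 points.

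| r | b + c | Paired half-width | Unpaired ÷ paired | Largest passing deficit (15 − half-width), unpaired / paired |
|---|---|---|---|---|
| 0 | 0.375 | 9.1 | 1.00 | 5.9 / 5.9 |
| 0.3 | 0.2625 | 7.6 | 1.20 | 5.9 / 7.4 |
| 0.5 | 0.1875 | 6.4 | 1.41 | 5.9 / 8.6 |
| 0.7 | 0.1125 | 5.0 | 1.83 | 5.9 / 10.0 |

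For rates from 90% down to 60%, the unpaired half-width runs from 6.3 to 10.3 points and the paired one at r = 0.5 from 4.4 to 7.3.

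**Power, Restylane 80%, Restylane Defyne 75%, r = 0.5.** The covariance is 0.5 × √(0.16 × 0.1875) = 0.0866, so both folds respond in 0.80 × 0.75 + 0.0866 = 0.6866, b = 0.1134 and c = 0.0634. The true SE is √[(0.1768 − 0.0025)/175] = 0.0316. The unpaired half-width is 1.96 × √(0.3475/175) = 0.0873 and the paired one 0.0619.
- Unpaired: Φ[(0.15 − 0.0873 − 0.05)/0.0316], about 66%.
- Paired: Φ[(0.15 − 0.0619 − 0.05)/0.0316], about 88% to 89%.

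Simulation with Wald intervals gives 66% and 88%. At r = 0.3 it gives 63% and 76%, and at r = 0.7 it gives 70% and 97%.

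**Power with equal rates.** At 75% and r = 0.5, simulation gives 96.4% unpaired and 99.5% paired. At 80% it gives 98.5% and 99.8%.

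**False non-inferiority.** At a true 15-point deficit (75% against 60%, r = 0.5), simulated error is 0.24% unpaired and 2.96% paired Wald, against a nominal 2.5%. Paired Wald reaches 4.2% at r = 0.7.

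**Imputing folds separately.** Take 10% of subjects with both folds imputed and, as an extreme, no correlation within imputed pairs. Discordance becomes 0.9 × (b + c) + 0.1 × 0.375:
- r = 0.3: 0.2738, half-width 7.59 to 7.75, up 0.2.
- r = 0.5: 0.2063, half-width 6.42 to 6.73, up 0.3.
- r = 0.7: 0.1388, half-width 4.97 to 5.52, up 0.5.

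In practice each fold's own earlier scores keep part of the correlation, while variation between imputations adds width. Simulated comparisons of separate with joint imputation gave increases of about 0.2 to 0.7 points.

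**The case against.** A reader might infer that the SAP prescribes an unpaired interval. It does not. A difference in response rates is also what a paired method estimates, (b − c) with b and c as above, so the sentence in SAP 2.4.3 fits either. Tables with N, n and rate per product are ordinary output for paired data too. The plan shows awareness of pairing elsewhere: FAS requires both folds injected, and SAP 2.8 drops baseline tables by product because each subject receives both. SAP 2.7 and protocol 10.10 are redacted, a redacted block follows protocol 10.4.1, and a paired method may be named there. All of this stands.

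A reader might also fear that the trial could pass wrongly. With positive correlation the reverse holds: the unpaired interval is too wide and the error rate falls well below nominal. If the products are truly equal, the power loss at r = 0.5 is only about 1 to 3 points. It is large only if Restylane Defyne is somewhat worse.

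On the PP items, the wording can be read as requiring both folds, the list is expressly not exhaustive, and SAP 2.4.2 expects missing data to affect both folds in most cases. That makes it a wording point with few subjects at stake.

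The imputation model is not answered by any of this. It is stated, it omits the opposite fold, and it is worse than a joint model that needs no extra data.

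**Conclusion.** The point holds as a gap in specification plus one stated rule that should change. The method for the deciding interval is not named in the analysis section, and the visible imputation model, result tables and PP wording do not carry the pairing. The documents do not support saying that an unpaired analysis is planned, or that a false non-inferiority claim is made more likely.

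If an independent-groups interval were used, it would be 20%, 41% and 83% too wide at correlations of 0.3, 0.5 and 0.7, and not at all at zero. Some positive correlation is likely, since the folds share a subject, preferably one evaluator, and the same baseline grade. At 75% response and r = 0.5, an observed deficit between about 5.9 and 8.6 points would pass or fail on the method alone, and a confirmatory rule should not leave that open. The imputation effect is smaller, roughly 0.2 to 0.7 points. All sizes rest on assumed rates, correlation and missingness. The paired power figures use Wald intervals, and a score interval would give up a little of that gain.

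**What to change.** Before database lock:
- **SAP 2.4.2:** impute with one row per subject, so that the earlier and Month 6 scores of both folds are imputed jointly.
- **SAP 2.4.3:** state that the 95% interval is for the within-subject difference in response proportions, using a paired score-type method (Tango, or Newcombe's paired method), since paired Wald is slightly liberal. For the five imputed sets, pool the paired difference and its paired variance by Rubin's rules, and say how the limits are formed from the pooled values. Use the same paired approach for PP, the sensitivity analyses and the site graphs.
- **Tables 8-1 and 8-2:** add the four response-pair counts (both folds, Restylane only, Restylane Defyne only, neither).
- **Table 2-1:** reword both WSRS items so that a subject missing the assessment for either fold is excluded from PP.

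If a redacted section already names a paired method, SAP 2.4.3 need only repeat it. The imputation, table and PP changes are still needed. The cost is SAP wording, table shells and some programming, with no new data.
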